Eligible participants will receive an email instructing them to complete an electronic consent form accessed through the program website and administered via Qualtrics. All participants who qualify will be sent a link to a Qualtrics survey containing a full consent form minus the signature line as well as a pdf document of the informed consent form minus the signature line for their records. Participants will indicate their consent and receipt of this consent form by indicating their informed consent on the Qualtrics survey. Participants who do not consent to participate will not be contacted further by the research team and all identifying information will be deleted from the records. Once informed consent is obtained, participants will be contacted regarding completion of the first assessment survey. Additionally, participants will be provided with a brief reminder of what participation in this study will entail and their rights as study participants prior to completing the pre-and-post surveys. Participants will be required to indicate their consent to proceed on the Qualtrics survey before the Qualtrics survey will allow them to view or respond to the survey questions. Participants will also be instructed to contact members of the research team with any questions regarding participation in each session.

Assessment and Session Protocols:

Once informed consent is obtained, participants will be contacted regarding completion of the first assessment survey (pre-assessment). Once the consent form and first survey are completed each participant will be assigned to a group led by one of the trained facilitators. Once assigned to a group, participants will be emailed with their zoom invitation. Participants will provide their physical mailing address on the first Assessment (Time 1). The project coordinator at UNC Charlotte will

mail the materials (handouts and slides) to each participant. After completing the CUIDANDO JUNTOS program, participants will be emailed a link to a post assessment Qualtrics survey. Participants will also be mailed a hard copy of their program completion certificate. Participants will also be asked to answer semi structured interview questions after completing the CUIDANDO JUNTOS program.

Data Analysis Plan:

Basic descriptive statistics for all outcome measures assessed both pre- and post-intervention. Internal consistency estimates, minimum and maximum scores, means and standard deviations are computed for each variable. To test for meaningful change over time, the change in mean score from Time 1 to Time 2 for each outcome measure was evaluated. Formal paired samples t-tests were conducted to test for statistical significance. However, given the small sample size and limited power, we also interpret Cohen's *d* as a more meaningful indicator of the magnitude of the observed effects.

Application Type
General Information
UNCC Personnel
Investigators Outside of UNCC
Conflict of Interest
Exemption
Research Location
Participants
Recruitment
Informed Consent Process
Study Methods and Procedures
Data Management
Benefits, Risks, Safety
Existing Data, Records, Specimens
Incentives and Costs
Study Attachments
PI Certification
Assignment
Review
All Pages

Application Type

Instructions

Before moving to the next page, carefully review the application type definitions listed below and then choose the application type that is appropriate for your research. This will populate the required protocol application pages for you to complete.

Application Type Definitions:

Initial Application: This application is for studies that will involve interaction, engagement, intervention, communication, etc. with human subjects. This may be direct or indirect (e.g., online surveys, use of survey panels, etc.) interactions.

Initial Application - Data Only: The application is for studies that will ONLY ever use data or biospecimens and NEVER have any direct interaction, engagement, intervention, communication, etc. with human subjects.

- Existing data refers to data you will receive or obtain from a source other than your study participant.
- Data obtained from secondary sources and not from the data collection procedures being proposed as part of this study.
- For example, if your study will involve existing data for secondary data analysis (e.g., student records, medical records, administrative data, etc.).
- Note, if you are conducting collaborative research and will be conducting data analysis for the larger collaboration, the IRB Reliance Agreement application type may be appropriate.
- Studies that will involve both the use of existing data and will involve additional procedures such as surveys, interviews, etc. do not use this application. Use the Initial Application type instead.

IRB Reliance Agreement: This application is only for use when UNC Charlotte will rely on an external IRB for the review and

Application Type Selection

* **Application Type:**

- ☒ Initial Application
- ☐ Initial Application - Data Only
- ☐ IRB Reliance Agreement

General Information

* Protocol #: IRB-24-0291	* Submission #: IRB-24-0291-01	Submission Type: Initial Application
-------------------------------------	--	--

Instructions

- When responding to question #2 below, state the goals of the proposed study as related to the research question(s).
- Provide a clear and succinct summary description of the background information that led to the plan for this project.

Title and Objective

* **1. Project Title:**
A Cultural Adaptation of the Caregiver TLC Psychoeducational Program to Support Latino Caregivers

- * **2. Objective/Aim: Using lay language, provide:**
- Background information and context
 - Rationale for why this study is needed
 - The study purpose, specific aims, or objectives that will be met by this specific project
 - Explanation of research questions and hypotheses being tested

You will be asked to describe the specific procedures in a later section of the application.

Background and Context information: There are several evidence-based interventions for distressed dementia caregivers that focus on skill building to increase resilience. However, few psychoeducational programs target Latino caregivers, and there are no evidence-based interventions promoting "social connectedness and support" in a culturally congruent way for Latinos. The Caregiver Thrive, Learn & Connect (TLC) is a telehealth caregiver educational program that builds upon evidence-based strategies from the "Coping with Caregiving" program (tested in REACH II) to improve caregivers' psychosocial outcomes. Caregiver TLC incorporates a goal-oriented approach focused on learning effective strategies to seeking support and connecting with caregivers and community resources. Dementia caregivers attend sessions in small groups through Zoom, making the program accessible for caregivers with limited information, time, transportation, and language proficiency. The program website allows caregivers to access information, resources (videos), attend informational activities (webinars) and participate in a virtual community where caregivers learn and connect with others.

Rationale: Several factors including distrust of the health system, language, and differences in cultural values contribute to the underrepresentation of Latinos in intervention research. There is urgency for culturally adapted programs addressing their needs. Our cultural adaptation follows the Barrera's Cultural Adaptation Behavioral Health Stage Model (2013).

Study Specific Aims: Specific Aim 1. To create a Community Advisory Board to engage Latino caregivers and community leaders to work with us to co-develop the program. Specific Aim 2. To test an early-stage adapted Spanish language of the program. Specific Aim 3. To examine the mechanism of social connectedness as a means to improve clinical outcomes (depression, stress, burden).

Research Questions and Hypotheses: This is a mixed model exploratory study to gather information from Latino bicultural and bilingual caregivers about their caregiving experience, the validity of the Spanish translation and acculturation of Cuidando Juntos program. We will gather qualitative data from Community Advisory Board members on the content and feasibility of the program. We also will collect basic quantitative data from a small pilot demonstration program using pre and post assessment of Latino caregiver participants. Our research questions will address the the level of acculturation and feasibility of the Spanish program Cuidando Juntos, and will provide an initial test for the efficacy of the small pilot study. Therefore, there are no specific quantitative hypothesis due to the descriptive and exploratory nature of the study.

Funding Source

- * **3. Is this activity funded, associated with a proposal/funding request, or will use University funds (e.g., startup, departmental, or discretionary funds)?**

☒ Yes ☐ No

3.1 If your funding source is in Niner Research, locate your grant record using the add button in the table below.

Proposal Name	Sponsor Name	Proposal Number

3.2 Use the table below to list all funding sources and requests that are currently NOT in Niner Research.

Funding Type	Sponsor (FRG, start-up funds, etc.)	Proposal Number (if available)	Department Name
--------------	--	--------------------------------	-----------------

Please upload the following documents (if available) on the "Study Attachments" page: Grant proposal, Scope of Work, Contract, and/or Agreement.

PI Status

* What is the primary status of the Principle Investigator (PI)?

- ☒ Faculty
- ☐ Staff
- ☐ Student

INSTRUCTIONS

- To add personnel: click the "Add" button in the top right corner of the Personnel table.
- Use the pop-up box to search by Last Name and First Name of the person you want to add.
- Choose the person from the list and click the "Select" button in the top right corner of the search box.
- Use the "Role" dropdown list to select the role for each person added.
- Important: You need to select a role for all Personnel using the Role dropdown box. For the Primary Investigator you select the "Primary Investigator" checkbox AND choose Primary Investigator in the "Role" dropdown.
- Repeat this process for all research team members.
- Any person listed on this page will be able to view and edit this record/application.

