Activities	 Obtain consent and/or assent  Perform research procedures  Administer study interventions or experiment  Obtain, use, or analyze identifiable or coded (has a study ID) data and/or specimens  Obtain, use, or analyze de-identified data and/or specimens  Other participant contact  Other responsibilities or roles
* Will the external institution and/or external collaborator defer review and oversight to the UNC Charlotte IRB?	Yes  No 
* Full legal name of external institution:	NA
* Federalwide Assurance (FWA) number from external Institution:	NA
* OHRP Registration Number of external IRB:	NA
* Contact Person at the external institution:	[name]
* Name, Title, Address, Phone, Email	[name]. [name]. [contact]. [contact]
* External institution signatory official:	Director of Human Subject Review Board at Rochester University
* Name, Title, Address, Phone, Email	[name], Administrator [contact]

Number of Participants

* 1. Total number of participants. 30

1.1 If this study will occur at multiple Research Locations (as listed on the Research Locations page), please specify the number of participants at each location/site. If this study is not occurring at multiple Research Locations state "Not Applicable."

All study activities will happen virtually using a zoom videoconference platform with HIPPA compliance

2. If the Total Number of participants listed above (question #1) includes multiple groups or cohorts of participants, please explain the number of participants for each group.

Cohort 1 = 10 participants will engage in a demonstration test of the program to further refine the content and design of the program in Spanish

Cohort 2 = 20 participants will engage in a pilot test for program to finalize the final version of the Spanish program.

Vulnerable or Select Populations

3. Do you have specific plans to include participants from these vulnerable or select populations? If so, check all that apply

☐ Children (under the age of majority for their location)

☒ Non-English-speaking

☐ Patients (i.e., have a specific disease, disorder or condition regardless of where they receive their healthcare)

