materials; each initial meeting will focus on one workshop session and feedback will be obtained on: how content is presented; appropriateness of examples and action plans; how to increase social connectedness -particularly with family members – within the context of that workshop's focus. The CAB will also review the program Website that is in English, and make recommendations to make it user-friendly for Latino caregivers. The CAB will recommend ways to use this website to increase social connectedness. CAB members need to identify as Latino, be bilingual, and have the necessary time and skills to participate. To meet Aim 2 (Stage 1B trial), based on this feedback, a preliminary adapted version will be tested in an Stage 1B trial (pre- post design). We will recruit 20 Latino caregivers and all will receive the intervention (with n=10 in each group, run sequentially). We will make refinements (if needed) based on participant and CAB feedback between the first and second group. We will collect qualitative and quantitative data with several metrics (described below). Caregivers need to be men and women, 45 years and older, who identify as primary caregivers of a PLWD with whom they co-reside or live close by. A stress rating will be used so that at least a moderate level of stress related to caregiving is endorsed. Willingness to complete interviews and surveys and provide feedback are also necessary. To address Aim 3, (mechanisms) we will assess changes in loneliness and social support and anticipate that Latino caregivers who demonstrate decreases in loneliness and increases in social support will experience lower stress levels, burden and depression.

6. Analytic Plans: We will collect qualitative and descriptive quantitative data using mixed methods: 1. Individual semi-structured interviews with members of the CAB to ask them about caregivers' needs, supportive services, cultural views and normative expectations about care. 2. Data from Focus Group participants on feasibility and acceptability of the adaptation and refinement. 3. Descriptive pre-post data from the early developmental trial (20 caregivers). Data Analytics.

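### Cohen's d is to be read as more meaningful than the paired t-tests because power is low, yet it has no interval and no stated standardiser, so chance-sized changes can pass as effects

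*Combined protocol and SAP*

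**What the plan says.** The Data Analysis Plan starts with descriptive statistics, then states that "the change in mean score from Time 1 to Time 2 for each outcome measure was evaluated" and that "Formal paired samples t-tests were conducted to test for statistical significance". It goes on: "given the small sample size and limited power, we also interpret" Cohen's d "as a more meaningful indicator of the magnitude of the observed effects". Neither there nor elsewhere in the text supplied is there a confidence interval for d or for the mean change, a definition of d, a rule for reading its size, a leading outcome or a multiplicity rule.

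Research Design item 6 (Analytic Plans) and the Project 9 Measures attachment list five scales given before and after the programme: Lubben-6, UCLA Loneliness, PSS-10, Zarit-6 and PHQ-9. The Background Questions also name two PROMIS scales, which the measures attachment does not list.

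On sample size, Research Design item 5 says "We will recruit 20 Latino caregivers and all will receive the intervention (with n=10 in each group, run sequentially". The IRB form gives "Total number of participants. 30", made up of a demonstration cohort of 10 and a pilot cohort of 20. On status, the Research Questions and Hypotheses section says "there are no specific quantitative hypothesis due to the descriptive and exploratory nature of the study", but also describes the work as a first test of efficacy.

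**The concern.** The reason given for leaning on d is "given the small sample size and limited power". With a small sample the observed mean change can lie well away from the true one. Dividing it by a standard deviation changes its units and leaves that uncertainty in place. If the divisor is the SD of change, d is the t statistic divided by the square root of n, so it says nothing about chance that the test has not already said.

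A d without an interval hides this. A small, non-significant value on any of five scales can be presented as a small effect. The undefined standardiser adds to the problem, because the same data can give different values of d. Item 7 of the Research Design calls the work preliminary to a Stage II efficacy proposal, so a chance-sized d could be mistaken for evidence of benefit when that trial is planned.

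**Working it through.** The plan states no power, effect size or SD, so there is no figure of its own to reproduce.

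**Inputs from the documents.** n = 20 (Research Design item 5) or 30 (IRB form total); five pre-post scales (Research Design item 6); single arm.

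**Assumptions, not in the documents.** Two-sided alpha of 0.05; no dropout; 0.2 as the value that would be called small; no true change.

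**1. Link between d and t.** With d = mean change / SD of change, t = d × √n. At n = 20, √n = 4.472 and the critical t on 19 df is 2.093. So p < 0.05 requires |d| ≥ 2.093 / 4.472 = 0.47. Values from 0.2 up to 0.47 are non-significant but can be read as effects.

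**2. Chance of |d| ≥ 0.2 on one outcome.** P(|t| ≥ 0.2 × √n) on n − 1 df:
- n = 20: P(|t| ≥ 0.894) = 0.382
- n = 30: P(|t| ≥ 1.095) = 0.282

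**3. At least one of five outcomes.** If independent, 1 − (1 − p)^5. For favourable changes only, replace p by p/2.

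| | n = 20 | n = 30 |
|---|---|---|
| Either direction | 1 − 0.618^5 = 91% | 1 − 0.718^5 = 81% |
| Favourable only | 1 − 0.809^5 = 65% | 1 − 0.859^5 = 53% |

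By simulation at n = 20 with outcomes correlated at 0.5, the figures are 85% in either direction and about 48% favourable only.

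**4. Effect of the standardiser.** With equal SDs and pre-post correlation r, d on the Time 1 SD is about √(2(1 − r)) times d on the SD of change. A threshold of 0.2 on the Time 1 SD therefore corresponds to 0.2 / √(2(1 − r)) on the SD of change. At n = 20, either direction:

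| Assumed r | √(2(1 − r)) | Equivalent threshold | One outcome | At least one of five |
|---|---|---|---|---|
| 0.8 | 0.632 | 0.316 | 17% | 61% |
| 0.5 | 1.000 | 0.200 | 38% | 91% |
| 0.3 | 1.183 | 0.169 | 46% | 95% |

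So at r = 0.8 a d of 0.30 on the Time 1 SD would be reported as 0.30 / 0.632 = 0.47 on the SD of change. At r = 0.3 the shift goes the other way: 0.30 / 1.183 = 0.25.

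**5. What an interval would show.** Exact 95% CIs from the noncentral t, SD of change, n = 20:
- d = 0.2: -0.25 to 0.64
- d = 0.3: -0.15 to 0.74 (p = 0.196)
- d = 0.5: 0.03 to 0.96 (p = 0.038)

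At n = 30, d = 0.3 gives -0.07 to 0.66.

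**The case against.** The sentence can be defended. The t-tests stay, d is only said to be read as well, and it is offered as an indicator of magnitude, which a p-value does not measure. No success rule, alpha or threshold for d is stated, and the study is labelled exploratory. Means and SDs are already to be reported, so the interval and the definition of d are what is missing. All of this stands, and it limits the point to how d is reported and read.

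A reader might infer more, and the documents do not support it:
- **That d replaces the test or is a second route to a declared success.** The plan declares no success criterion.
- **That moderate or large effects are equally open to this misreading.** On the SD of change with n = 20, d = 0.5 already gives p = 0.038. The problem lies below about 0.47, unless a single group of 10 is analysed or dropout is material.
- **That 91% is the chance of a spurious benefit.** It counts worsening as well as improvement, assumes independent outcomes and depends on the standardiser.
- **That these d values will be used to size the next trial.** The documents say only that this work is preliminary to it.

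The exploratory label relaxes the need for multiplicity control. It does not remove the need for an interval, since the same section speaks of an initial efficacy test.

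**Conclusion.** The point holds as a fault in how d is reported and interpreted. Low power is given as the reason to treat d as more meaningful than the test, although d carries the same sampling error, and nothing in the plan displays that error. With no true change and n = 20, a favourable d of at least 0.2 on one or more of five scales has a chance of 65% if the scales are independent and about 48% if they correlate at 0.5. The two-sided figure is 91%, or 61% to 95% on the Time 1 SD for r between 0.8 and 0.3. At n = 30 it is 81% on the SD of change.

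These figures rest on the assumed 0.2 threshold, complete data and a true change of exactly zero. That last assumption may be generous to the plan: entry can depend on an elevated PSS-10, which is also an outcome, so regression to the mean could produce improvement on that scale without any programme effect. For the same reason it would be wrong to infer that an interval excluding 0 establishes benefit. In a single-arm pre-post study it establishes change only.

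**What to change.** Replace the sentence on Cohen's d in the Data Analysis Plan so that it commits to the following:

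1. For every outcome, report the mean change in scale units with its 95% CI.
2. Report d with a stated standardiser (for example the Time 1 SD), a small-sample correction and a 95% CI.
3. Label all p-values exploratory.
4. Draw no conclusion of benefit from d alone. State that even an interval excluding 0 shows pre-post change and not an intervention effect, because there is no control group and entry can depend on an elevated PSS-10.
5. A leading outcome is optional. If one is given priority, choose it before the data are seen. The section is partly in the past tense, so if the analysis has already been done, disclose that the choice was made afterwards.

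The cost is a change of wording and a few lines of code, with no new participants, visits or measures. The downside is a little more analysis work and results that look less favourable.

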- Exemption means that the full scope of the regulations do not apply. However, the ethical requirements for Human Subjects Research do apply. (e.g. voluntary, consent is obtained, privacy and confidentiality are protected, etc.)
- Studies involving drugs, devices, medical procedures, experimental interventions or manipulations, or greater than minimal risk are NOT eligible for Exemption.
- Research involving prisoners may not be eligible for Exemption.
- For additional guidance on Exemption categories please check the Resource Bar.

Exemption Screening

* 1. Do you want your study evaluated for possible Exemption determination?

☐ Yes ☒ No

In order to be eligible for Exemption approval determination, your research must fit an Exemption category. All of the categories will be listed. Only select the applicable category. You MUST complete the explanation narrative for the category you select to provide rationale and justification for why the category applies to your research.

Instructions

- If you are conducting research where participants have a reasonable expectation of privacy (public school, daycare center, medical facility), you must upload a letter of support from the facility administrator.
- Some public school systems have their own research review process. Please check with a school system representative to ensure you are meeting local requirements.
- If you are recruiting participants from other universities, they may require local IRB review. Please check with the institution's IRB office to ensure all local requirements are followed.
- If the location is outside the US, you must provide documentation that you meet requirements for conducting human subjects research based on that country's laws.
- If you will conduct study activities at/on the UNC Charlotte campus, you can list UNCC campus as the Site Location and yourself as the Site Contact. If the study will be conducted entirely online, you can list the location as Online (Zoom, Qualtrics, etc.) with yourself as the Site Contact.
- List the school location if you are conducting the study at school (K-12, University, etc.). List the local community organization if the study will occur at such a site.
- If you will recruit study participants from a business/company/organization, you would list the site location accordingly. The Site Contact would be the person you have approval from to conduct recruitment.

Locations

* 1. Will this study be conducted in locations outside the United States?
